Study Protocol and Statistical Analysis Plan

A Study to Compare Patient Perceptions of Two Different Hearing Aid Processing Philosophies

Version 1.0

September 13 2021

NCT04839289

Protocol Title

1 Background

Hearing aid brands vary in their DSP (Digital Signal Processing) strategies. For example, there are philosophical differences in processing when there is uncertainty of target location. One processing strategy aligns with a front facing target, whereas another aligns with the absence of a target in these situations. Despite the investigations regarding the different processing strategies, research has been limited as to how different populations perceive these different strategies in their daily life. Previous data gives insight to the different strategies in lab environments and simulated acoustic environments, but there is substantial need to investigate how these findings relate to the real world, which this study seeks to accomplish through the use of a home trial comparison.

2 Objectives

The primary objective of this study is to investigate whether individuals with moderate to severe hearing loss perceive a difference between Brand A and Brand B devices in their daily life.

3 Description of the investigational device

The investigational devices are intended for consumers with hearing loss, and provide amplification for soft, medium, and loud inputs using varying methods of compression and features. The devices will be used as intended for this investigation.

4 Design of the clinical investigation

This interventional study uses a within-subject, single blinded design with three conditions: Condition one consists of study hearing aid set A, condition two is study hearing aid set B, and condition three is study hearing aid set C. Sets A and C are the same hearing aids but will be different color casings. Twenty participants are planned.

5 Risks and benefits of the investigational device and clinical Investigation

Hearing aids enable people to hear sounds again, which could not be heard previously due to a hearing loss. The benefit of a compensated hearing loss results in a facet of multiple benefits which can be measured in different dimensions.

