One of the main benefits of hearing aids is that they may enable people with a hearing loss to better and easier hear speech again, which is a fundamental ability to communicate and interact with others (e.g. family and friends, colleagues at work) in different listening situations in daily life.

The investigation carries risks typical to the standard of care for fitting and placing hearing aids in the ear. When placing a dome in the auditory canal, there is the risk of discomfort to the participant. There are risks of skin sensitivity to the material of the devices inserted into the auditory canal and behind the ear (pinna).

The risks of this study are minimal as the procedures are within the scope of practice of the

research audiologists. The participants may notice an improvement in hearing as compared to their own devices, or they may prefer their own devices to the study devices. The primary endpoint of subjective questionnaires and calculation of the Net Promoter Score will provide evidence for the perceived similarities or differences between the two study devices, as well as any preference for either device.

6 Endpoints

- SSQ (Speech Spatial Qualities) Questionnaire: Subjective ratings from 0 to 10 on various aspects of hearing aid performance in daily life, hearing speech in a variety of situations and contexts, spatial hearing, and overall qualities of hearing.
- Hearing Aid Satisfaction Score: Subjective ratings on overall satisfaction of devices. Ratings range from Very Satisfied (5) to Very Dissatisfied (1) for a number of hearing aid features, as well as performance in various listening situations.

7 Inclusion and Exclusion Criteria

Inclusion criteria for participant selection:

1. Experienced (6+ months) Phonak hearing aid users
2. N3-N4 binaural sensorineural hearing loss
3. Age 18 years and older

Exclusion criteria:

1. Conditions which may cause fluctuations in hearing (i.e. Meniere's)
2. Unable to tolerate the physical fit of RIC device with standard fit domes
3. Unable or unwilling to wear study devices for specified period of time, or inability to be seen for 4 study visits

8 Measurements and procedures

This study has a total of four visits.

Visit 1	Visit 2 (following Home Trial #1)	Visit 3 (following Home Trial #2)	Visit 4 (following Home Trial #3)

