-Sound Quality Questionnaire for own devices -Hearing Aid Satisfaction survey for own devices -Three sets of hearing aids programmed for participant -Participant leaves with set A for home trial #1	-Sound Quality Questionnaire for Set A -Hearing Aid Satisfaction survey for Set A -Participant returns Set A and is sent home with Set B for home trial #2	-Sound Quality Questionnaire for Set B -Hearing Aid Satisfaction survey for Set B -Participant returns Set B and is sent home with Set A (Participant is told this is set C) for home trial #3	-Sound Quality Questionnaire for Set A -Hearing Aid Satisfaction survey for Set A -Participant returns set A and exits study

9 Statistical design and analysis

Fifteen to twenty participants are needed to determine significant differences between the study set A device and study set B device algorithms and sound quality. As the null

hypothesis (no difference will be detected) is the expected outcome, a smaller number of participants is acceptable. As this is an exploratory study, no a priori power analysis has been done.

Data collection will terminate once the acceptable number of participants has been recruited and have completed all three trials. As this is an observational study and done for internal purposes only, there is no statistical criteria for termination.

There are no planned objective tests for this study, therefore, all data collected will be subjective and qualitative in nature. Responses will be collected as question, response, and anonymous participant ID.

Responses to the subjective questionnaires will be analyzed using a repeated measures ANOVA test. The mean scores for each subsection of the sound quality questionnaire will be analyzed between the three test devices for all participants. The mean scores of each subsection of the sound quality questionnaire will also be analyzed between the three sets of study devices for all participants. Repeated measures ANOVA will also be used to determine if there are any individual differences between the brands. Aggregate data and individual HASS data will be analyzed using repeated measures ANOVA.

10 Investigation Duration

The expected duration of participation is six weeks.

11 Data Handling and Management

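### Section 9 assigns individual brand differences to a repeated measures ANOVA, which compares group means and counts participant-by-set variation as error

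*Combined protocol and SAP*

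**What the plan says.** Section 2 gives the primary objective as to "investigate whether individuals with moderate to severe hearing loss perceive a difference between Brand A and Brand B devices in their daily life". Section 4 describes three conditions and states: "Sets A and C are the same hearing aids but will be different color casings". By the visit table in Section 8, every participant wears A, then B, then A again under the label C. Each set is handed back before the next is issued, and both questionnaires are completed after each trial.

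Section 9 names one method throughout. Repeated measures ANOVA is applied to mean subsection scores across the three sets, to the HASS data in aggregate and individual form, and to a separate individual-level aim: "Repeated measures ANOVA will also be used to determine if there are any individual differences between the brands".

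Section 5 says that the questionnaires and a Net Promoter Score will give evidence on perceived differences "as well as any preference for either device". The Net Promoter Score appears neither among the endpoints in Section 6 nor in the visit table, and Section 9 plans no analysis of it or of preference. Section 9 also treats the null as likely, saying that the null "hypothesis (no difference will be detected) is the expected outcome, a smaller number of participants is acceptable".

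**The concern.** In a one-way repeated measures ANOVA with one score per person per set, a participant's general tendency to rate high or low is removed. What remains as error is the participant-by-set interaction, which is the extent to which a person's ratings favour one set over another. That is the quantity the quoted sentence sets out to find. The more participants diverge, the larger the error term and the harder it is to reject.

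Opposite leanings are conceivable when two processing philosophies are compared. If they occurred, the mean comparison could be flat although many participants noticed a difference. A flat result is also the expected one, so it would prompt no further look. The design already holds a yardstick, since the same device is rated twice under two labels, but Section 9 does not use it.

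**Working it through.** **Inputs.** From the documents: three sets worn in the order A, B, A (labelled C). On numbers, Section 4 has "Twenty participants are planned" and Section 9 has "Fifteen to twenty participants are needed to determine significant differences between the study set A device and study set B device algorithms and sound quality". The second figure cannot be reproduced: no alpha, SD or effect size is given, and Section 9 says "no a priori power analysis has been done". Assumed for illustration: alpha 5%, independent normal rating error with SD σ = 1 point, and each participant's true B-minus-A difference equal to +d or −d.

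**ANOVA by hand, n = 20, d = 2.** A shift of ±d on B alone moves a person's three scores by (−1/3, +2/3, −1/3) × d around that person's own mean, a sum of squares of (2/3)d². If m is the mean shift over participants:

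- expected set mean square = 1 + n(2/3)m²/2
- expected error mean square = [38 + n(2/3)(d² − m²)]/38, where 38 = 2 × 19
- critical F on 2 and 38 df = 3.24

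| Split | m | Set MS | Error MS | Ratio | Simulated rejection |
|---|---|---|---|---|---|
| 10/10 | 0 | 1.00 | (38 + 53.3)/38 = 2.40 | 0.42 | 0.1% |
| 13/7 | 0.6 | 1 + 4.8/2 = 3.40 | (38 + 48.5)/38 = 2.28 | 1.49 | 8% |
| 15/5 | 1.0 | 1 + 13.3/2 = 7.67 | (38 + 40)/38 = 2.05 | 3.74 | 56% |
| 20/0 | 2.0 | 1 + 53.3/2 = 27.67 | 1.00 | 27.67 | 100% |

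At 14/6 and 16/4 the simulated rates are about 26% and 83%. With nobody perceiving a difference the rate is 5%. At the balanced split it is therefore lower when everyone perceives a 2-point difference than when no one does. If each person's direction is random at 50/50, the rate is 5.3% for d = 1 and 6.5% for d = 2 (4.6% and 5.0% with Greenhouse-Geisser correction), about the false-positive rate.

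**What the repeated device allows.** For each person take D1 = B − (A + C)/2 and D2 = A − C. Without individual brand effects, Var(D1) = 1.5σ² and Var(D2) = 2σ². Then F = [Var(D1)/1.5]/[Var(D2)/2] on n − 1 and n − 1 df tests for participant-by-brand variance. At 10/10 and d = 2, the ±2 effects have sample variance 4 × 20/19 = 4.21, so the expected numerator is (1.5 + 4.21)/1.5 = 3.81 against 1, with critical value 2.17. Simulated rejection with n = 20 and a 10/10 split is 30%, 68% and 93% for d = 1, 1.5 and 2, and 5% for d = 0. With n = 15 (8/7) and d = 2 it is 85%, against 0.2% for the ANOVA.

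**Limits of that test (n = 20, assumed inputs).**

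- All participants share the same difference: it rejects in 5%, while the ANOVA rejects in 89% (d = 1) to 100% (d = 2).
- Rating error varies between people (log-normal, log-SD 0.3 to 0.7), no brand effect: false positives of 7% to 15%.
- A person-specific second-period effect of SD 0.5 or 1, no brand effect: rejection in about 9% or 29%.
- Steady individual drift of SD 0.5 per period: it cancels in D1 but inflates D2, and power at d = 2 falls to about 67%.

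**The case against.** The objective can be read as a question about a population. The Background speaks of how populations perceive the strategies, and Section 9 analyses means over all participants. On that reading a test of means is a proper test of the objective. This stands, and it rules out saying that the main analysis misses the objective. It does not rescue the quoted sentence, which sets an individual-level aim of its own.

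The word individual is also undefined. It might mean single items, pairwise comparisons, or an ANOVA within each participant using items as replicates. The last would not have the error-term problem, but nothing in Section 9 describes it, and the first two still compare group means.

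A reader might infer that no statement of preference is collected. The documents do not settle that: Section 5 mentions preference and the Net Promoter Score, and the questionnaire items are not reproduced. What can be said is that the visit table lists no comparative question and Section 9 gives preference no analysis.

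Finally, the variance-ratio test has the weaknesses shown above, so it should not stand as the sole replacement. The study is also described as exploratory and internal, and the participant-level analysis could be run later on data already planned. Both points lower the urgency.

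**Conclusion.** The concern holds in a limited form. As specified, the ANOVA cannot determine individual differences between the brands, and no other part of the plan supplies a participant-level analysis. The size depends on how leanings divide: near-total cancellation at an even split, partial at unequal ones, none when all lean the same way. The percentages rest on an assumed SD, alpha and effect size; the documents give none of these.

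A reader might infer that the study will report no difference although every participant perceived one. The documents do not support this. Nothing in them indicates a balanced split, and Section 9 does not say that a non-significant result will be reported as showing that individuals perceive no difference. This is a worthwhile low-cost correction, not a must-fix.

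**What to change.** 1. Keep the mean comparison, stated as the test for a brand difference shared across participants.
2. Replace the sentence on individual differences with a supplementary exploratory analysis: for each subsection, report every participant's B − (A + C)/2 beside the spread of the A − C gaps, with the variance-ratio F test as optional support.
3. State its limits. It detects heterogeneity and not a shared difference. It assumes similar rating error across participants. Because B is always worn second, it cannot separate individual brand effects from individual period effects or drift.
4. Add one Visit 4 item asking whether the participant noticed a difference between the sets and which was preferred (A, B, C, none), with the A-versus-C answers as the control.
5. State that a non-significant mean comparison does not show that individuals perceive no difference.

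The cost is some rewording of Section 9 and one question at the last visit, with no extra participants or visits. Only the Visit 4 item has to be in place before data are collected. Power for small individual differences stays modest (30% at d = 1 in the balanced illustration).

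### Section 9 answers one brand question with several repeated measures ANOVAs, and states no significance level, adjustment, primary score or brand contrast

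*Combined protocol and SAP*

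**What the plan says.** Section 2 sets one objective: whether users perceive a difference between the two brands in daily life. Section 4 makes sets A and C the same hearing aid in different casings, so the three sets represent two brands. Section 8 gives every participant A, then B, then A again under the label C.

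Section 9 names one method for everything: "Responses to the subjective questionnaires will be analyzed using a repeated measures ANOVA test". For the sound quality questionnaire, "The mean scores for each subsection of the sound quality questionnaire will be analyzed between the three test devices for all participants". The next sentence nearly repeats this: "The mean scores of each subsection of the sound quality questionnaire will also be analyzed between the three sets of study devices for all participants". It is unclear whether that is a second set of tests. Repeated measures ANOVA is also to be used to look for individual differences between the brands. For the satisfaction survey, "Aggregate data and individual HASS data will be analyzed using repeated measures ANOVA".

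The number of tests is not given. Section 6 describes the SSQ as covering "hearing speech in a variety of situations and contexts, spatial hearing, and overall qualities of hearing", which suggests three subsections, and the satisfaction ratings as given "for a number of hearing aid features, as well as performance in various listening situations", without a count. Section 5 treats the questionnaires together with the Net Promoter Score as the primary endpoint. No section states a significance level, an adjustment, a primary score, or a contrast between the brands.

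**The concern.** A yes/no question is answered by a list of tests, with no statement of which result, or how many, would count as a perceived brand difference. The plan expects to find no difference. If that expectation is right, every significant result is a false positive, and there is no rule for discounting one or for preventing a choice among results afterwards.

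There is a second gap. A three-set ANOVA asks whether any of A, B and C differ, which is not the brand question. Because A and C are the same device, a significant result can come from A versus C alone. The plan needs both a rule for the number of tests and a contrast that isolates the brand.

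**Working it through.** **Plan's own figure.** There is none to reproduce: the plan gives no significance level, effect size, standard deviation or error rate.

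**Inputs.** From the documents: 15 to 20 participants (Section 9; 20 planned in Section 4), three sets, one ANOVA per subsection, one HASS aggregate. Assumed: 0.05 per test; three subsections (inferred from Section 6); 10 to 30 HASS items if items are tested; a common correlation between scores of 0.3 to 0.7, with 0.9 as a check.

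**Independent tests.** The chance of at least one p<0.05 among k independent true-null tests is 1 − 0.95^k.
- k=4 (three subsections and the HASS aggregate): 1 − 0.95^4 = 18.5%
- k=14: 51.2%; k=20: 64.2%; k=30: 78.5%
- 50% needs k = ln 0.5 / ln 0.95 = 13.5

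**Correlated scores.** Ratings by the same people are likely to be positively correlated, which lowers these figures. Simulated three-set ANOVAs with identical devices, n=20, 4,000 runs per cell:

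| Tests | corr. 0.3 | 0.5 | 0.7 | 0.9 |
|---|---|---|---|---|
| 4 | 18% | 15% | 13% | 10% |
| 14 | 44% | 37% | 26% | 14% |
| 20 | 56% | 45% | 31% | 16% |
| 30 | 68% | 54% | 37% | 18% |

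Results at n=15 are within about 2 points. Over repeated simulations at n=15 and n=20, the four-score figure for correlation 0.3 to 0.7 ranged from 12% to 19%. Adding 10, 20 or 30 items to the four scores gave 26–47%, 34–61% and 38–71%, or roughly 25–70% overall.

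**How much of this is about the brand.** For one test at n=20 with no true difference (40,000 runs), 5.2% of omnibus tests rejected, but only 2.6% also showed B differing from the A/C average at p<0.05. Requiring both conditions roughly halves the four-score figure, to about 7–9%. Section 9 does not require both. Nor is naming a contrast enough on its own: four unadjusted A-versus-B contrasts at n=20 gave 14–18%.

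**Power under the fix.** Assume a shift of 0.66 SD of the paired A−B difference in one score. This effect size is not in the documents. With independent, equal-variance within-person errors of SD σ, the shift is 0.66 × √2 σ = 0.933σ.
- B versus the mean of A and C: the contrast has SD √1.5 σ = 1.225σ, so the standardised shift is 0.933/1.225 = 0.762. The first Holm step tests at 0.05/4 = 0.0125. Noncentral t power: about 73% at n=20 and 55% at n=15.
- Unadjusted omnibus test: noncentrality n × (2/3) × 0.933², which is 11.6 at n=20 and 8.7 at n=15. Noncentral F power at 0.05: about 84% and 71%.

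**The case against.** The best defence is that Section 9 calls the study exploratory and for internal use, and Section 19 limits reporting to an internal report. Strict familywise control is not obligatory in such work. This stands as a reason to keep the remedy light. It does not remove the problem, because the same section says "Fifteen to twenty participants are needed to determine significant differences between the study set A device and study set B device algorithms and sound quality", and a plan that intends to find significant differences needs to say what counts as one. That sentence justifies the sample size and is not a decision rule; but there is no decision rule anywhere else.

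Four further points stand and limit the claim:
- No significance level is stated, so testing at an unadjusted 0.05 is inferred from silence.
- Section 9 speaks of a sound quality questionnaire and never expressly equates it with the SSQ of Section 6, so three subsections is also an inference.
- Omnibus rejections include chance differences between A and C, so the omnibus figures overstate the chance of a specific brand claim if significant tests are followed up properly.
- A stricter threshold makes the expected null result easier to obtain. That is a real cost in a small study, and the fix should be judged with it in view.

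**Conclusion.** The point holds in a conditional form. Section 9 runs several tests on one question and gives no level, adjustment, primary score or brand contrast. At an assumed 0.05 per test with identical brands, the chance of at least one false-positive omnibus test is about 12–19% for the four inferable scores at correlation 0.3–0.7, and about 10% at 0.9. It is higher, roughly 25–70%, if 10–30 HASS items are tested separately, and only part of those rejections would also separate B from A and C.

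A reader might infer that a false brand difference is about as likely as not. The documents do not support that: it needs about 14 independent tests, or nearly 30 at correlation 0.5, and the number of HASS items is not given. A reader might also take *individual* to mean one test per participant and quote 1 − 0.95^15 = 54% to 1 − 0.95^20 = 64%. That reading is possible, but a significant result in one person is not an error about the group-level objective, and the independence and 5% validity of such tests are assumed.

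**What to change.** In Section 9:
- State a familywise level of 0.05 and base the brand conclusion on one contrast: set B minus the mean of the two set A periods (A and C).
- Apply it to the subsection means and the HASS aggregate as one family, with Holm or a sign-flip max-T permutation test. List the subsections, and confirm which questionnaire they belong to.
- Report A versus C as a negative control. The device is the same, so a difference there reflects chance, time or expectation.
- Report individual HASS items and individual participants as estimates with confidence intervals and no significance claim.
- Remove or explain the near-duplicate subsection sentence, and say whether the Net Promoter Score is descriptive. If it is to be tested, it joins the family, and with three subsections the first Holm step becomes 0.05/5 = 0.01.

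The contrast must be spelled out because set A is worn twice. In the fixed order A, B, C, averaging the first and third periods also cancels a linear time trend, though not a curved one.

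The cost is analysis wording and a few lines of code, with no extra participants or visits, and some power. For the assumed 0.66 SD shift in a single score, power at the first Holm step is about 73% at n=20 and 55% at n=15, against about 84% and 71% for the unadjusted omnibus test.
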